1. Title Page

Protocol Title: Fluoxetine's effects on attention and emotional memory in anxious and depressed youth and adults.

Protocol Number: 01-M-0192 Date of This Submission/Version: May 11th, 2023

Principal Investigator

	[name]	SDAN/NIMH	[name]	[contact]	[contact]

Total requested accrual

Subjects of Study	Total to be recruited	Total to be studied	Sex	Age Range
Children and adolescents with a anxiety disorder	n 600	150	M & F	8-17
Children and adolescents with major depression	80	60	M & F	8-17
Psychiatrically healthy children and adolescents	750	150	M & F	8-17
Adults with major depression	150	100	M & F	18-65
Adults with an anxiety disorder	200	60	M & F	18-65
Psychiatrically healthy adults	750	150	M & F	18-65
Total participants in study	2530	670		

Project Uses Ionizing Radiation: 🖾 No 🛛 🗆 Yes (attach *RSC/RDSC documentation*)

- □ Medically-indicated only
- □ Research-related only
- Both

IND/IDE Drug/Device/#NSR Sponsor:NIMH	□No		⊠Yes ((attach FDA documentation)
Durable Power of Attorney Multi-institutional Project	🗵 No	🗵 No	□ Yes	□Yes
Data and Safety Monitoring Board	🗵 No		□ Yes	
Technology Transfer Agreement Agreement type and number _	🗵 No		□ Yes Expira	ation Date
Confidential Disclosure Agree	ement	🗵 No		□ Yes
Samples are being stored		□ No		🗵 Yes

2. Table of Contents (page numbers) Face Page	1-3
Table of Contents	
Precis	
Introduction	6-8
Study Objectives or Hypotheses	8-9
Subjects	9-11
Study Design & Methods	11-37
Risks/Discomforts	37-42
Subject Monitoring	42-43
Outcome Measures	43
Statistical Analysis	43-48
Human Subjects Protection	48-52
Benefits	52-53
Consent Documents and Process	53-54
Data and Safety Monitoring	54-55
Quality Assurance	55
Adverse Event Reporting	55
Alternatives to Participation	56
Privacy	56
Confidentiality	56-57
Conflict of Interest	57
Technology Transfer	57
Research and Travel Compensation	57-58
References	58-65

3. Precis

Objective: This protocol uses functional magnetic resonance imaging (fMRI) and magneto- and electroencephalogram (M/EEG) to examine neuro-cognitive correlates of pediatric and adult mood and anxiety disorders. The primary goal of the project is to document, in pediatric anxiety disorders and major depression, perturbations in brain systems mediating attention biases, fear conditioning, emotional memory, and response to various forms of motivational stimuli. As one secondary goal, the project measures the relationship between these factors and treatment response to either fluoxetine, a specific serotonin reuptake inhibitor (SSRI), or cognitive behavioral therapy (CBT). Another secondary goal examines similar associations in adults.

Study Population: A total of 2530 children, adolescents, and adults will be recruited. Most subjects will not be able to complete all procedures. We seek to comprehensively study 150 juveniles with only a current anxiety disorder, 60 juveniles with current major depression, 150 juveniles with no psychiatric disorder, 100 adults with major depression, 60 adults with an anxiety disorder, and 150 adults with no psychiatric disorder. To achieve this, we are recruiting 2530 individuals.

Design: Subjects will be tested using fMRI and M/EEG paradigms designed to examine brain regions engaged when processing motivationally salient stimuli, as assessed during attention, memory, social interaction, reward, and fear-conditioning paradigms. After these initial fMRI and M/EEG tests, subjects with depression or an anxiety disorder receive treatment. Treatment will comprise open treatment with either fluoxetine or CBT, augmented with computer-based attention retraining, delivered in a randomized-controlled design, with random assignment to either active or placebo attention-training regimens. Adolescent subjects then will be re-tested after eight-weeks using only the attention, memory, and conditioning paradigms.

Outcome Measures: Prior imaging studies note that tasks requiring attention modulation, emotional memory, social interchange, and fear conditioning engage brain regions previously implicated in adult mood and anxiety disorders. These regions include most consistently the amygdala and ventral prefrontal cortex. Moreover, imaging studies of reward function implicate the striatum and prefrontal cortex in adult mood disorders. *As a result, we hypothesize that attention, memory, social interaction, reward, and conditioning paradigms will engage the amygdala, ventral prefrontal cortex and striatum in both psychiatrically healthy and impaired subjects. Moreover, we hypothesize that these healthy and psychiatrically impaired groups will differ in the degree of engagement.*

Juvenile subjects also will be treated for eight-weeks, and a subset will be re-tested with fMRI and M/EEG. We predict that pre-treatment abnormalities in neural circuitry will predict response to treatment, such that increased amygdala and prefrontal activation will occur in individuals who show the strongest response to treatment. Moreover, we hypothesize that effective treatment will normalize abnormalities in attention and emotional memory, as manifest in fMRI and M/EEG measures.

4. Introduction/Scientific Rationale

Three areas of research inform this protocol - - research on: i) associations among pediatric and adult mood and anxiety disorders;¹⁻¹¹ ii) neuro-cognitive correlates of adult mood and anxiety disorders;¹²⁻³³ as well as iii) neuro-cognitive correlates and treatment of pediatric mood and anxiety disorders.³⁴⁻⁴⁷

4.1. Associations among pediatric and adult mood/anxiety disorders

4.1.1. Comorbidity: Most children with an anxiety disorder suffer from multiple disorders^{1, 4, 5, 7-9}. Comorbidity is particularly strong among social phobia, separation anxiety, and generalized anxiety disorders.⁴ Such comorbidity complicates studies on risk factors and treatments. As a result, most current treatment and risk factor research on childhood anxiety disorders groups together the diagnoses of social phobia, separation anxiety disorder, and generalized anxiety disorders.^{1, 3-5, 7-9, 48} In fact, virtually all treatment trials combine the three diagnoses into a single category.^{5, 48} The current protocol will combine these three conditions into one anxiety group. There also is considerable comorbidity between childhood anxiety and depressive disorders. This further complicates studies on disorder-specific correlates. The current protocol compares healthy youth with two patient groups: i) youth with any one of three anxiety disorders (social phobia, separation anxiety disorder, and generalized anxiety disorder) in the absence of depression; and ii) youth with depression, with or without anxiety. Sub-analyses also will contrast depressed subjects with and without anxiety disorders and subjects with specific anxiety disorders.

4.1.2. Associations Between Disorders in Children and Adults: Youth with mood or anxiety disorders face a two-to-five fold increased risk for adult depressive and anxiety disorders.¹⁻¹¹ In fact, most adults with a mood or anxiety disorder had shown previous signs of a mood or anxiety disorder during childhood.^{1, 4, 5, 8} Youth with various mood and anxiety disorders also show high familial loading for mood and anxiety disorders.^{2, 6, 10, 11} Parental history of a mood or anxiety disorder may represent the most potent risk factors for personal history of a disorder in a child.⁷ Based on such data, recent studies on pathophysiology of adult mood and anxiety disorders provide insights on pathophysiology in pediatric conditions.

4.2. *Cognitive processes and brain circuitry in adults:* Mood and anxiety disorders are associated with cognitive abnormalities that may result from disruptions in neural circuits regulating attention and memory.

4.2.1. Attention: A wealth of research documents enhanced attention to threat in adult anxiety disorders. Both basic and clinical studies elucidate factors that produce such effects. Adult anxiety disorders involve enhanced attention bias for threat cues.^{19-21, 23-27, 29, 32, 49} Attention bias is demonstrated in various tasks, including interference^{9, 28, 32, 47, 49} and orienting tasks.^{9, 28, 47, 49} In general, orienting tasks better isolate brain circuits involved in attention modulation.^{27, 28}As a result, the current protocol relies on orienting tasks. While enhanced attention bias is most consistently found in anxiety, effects emerge with less consistency in depression.^{19, 27, 28} Interestingly, the time course of bias differs in anxiety and depression. Bias in anxiety but not depression occurs with short presentation of emotional cue stimuli (17-33 msec), whereas enhanced attention bias in Mogg and Bradley,^{19, 27, 28} the current protocol elicits attention bias by presenting emotionally evocative facial cue stimuli at both long and short exposures.

Because attention bias can be reliably generated in animals through fear conditioning experiments, common brain structures are thought to regulate aspects of attention bias and fear conditioning.^{24, 25, 50-52} This includes the amygdala and ventral prefrontal cortex. Imaging studies in humans note the engagement of these structures during attention bias paradigms.⁵³⁻⁵⁶ For example, angry faces that affect attention in orientation paradigms consistently engage ventral aspects of the prefrontal cortex, a region strongly implicated in mood and anxiety disorders.^{53, 55-57}

In humans, effective treatments normalize attention bias associated with anxiety.^{25, 27, 32} In animals, anxiolytics reduces attention bias for fear-related stimuli.⁵⁸⁻⁶⁰ Neuroimaging studies suggest that medications

could exert such effects by altering functioning in the amygdala and ventral prefrontal cortex.^{61, 62} Finally, most studies of fear conditioning and attention rely on relatively simple paradigms with questionable ecological validity. Considerable recent interest has emerged in adapting reward or social-interaction paradigms to provide attention-related tasks with stronger ecological validity. Moreover, these tasks also rely on a range of aversive stimuli to evoke attention. This has raised major questions on the degree to which enhanced attention responding to threat represents enhanced sensitivity to a relatively narrow or broader range of threatening stimuli, as occurs across anxiety disorders or to unique subsets of patients.

¹¹¹⁻¹¹⁵Currently, most research in this area relies on words or pictures. However, abnormal attention to physiological perturbations generally manifests with larger effect sizes than abnormal attention to words or pictures. More work is needed that compares responses among the various picture-based and physiologic paradigms. ¹¹² This includes studies attempting to replicate findings on abnormal responding to social stimuli in social anxiety disorder, as opposed to abnormal responding to respiratory stimuli in separation anxiety disorder. Such disorder-general and disorder-specific responses can be contrasted with the dot-probe task, fear-conditioning paradigms, and CO2 inhalation, a paradigm eliciting particularly large, consistent, and relatively specific between-group differences in research on separation anxiety disorder.

In work on attention, paradigms often attempt to elicit anxiety-related attention problems that arise under the stress of a cognitive task. This interest in stress-evoked attention perturbations reflects a view that hypersensitivity to stress is an important characteristic of anxiety disorders. Beyond assessing anxiety symptoms, this protocol also uses clinical measures to assess the sensitivity of children and adolescents to stressful events, which can also impact performance on the paradigms used in the protocol. The COVID-19 pandemic of 2020 enhanced the level of stress that children enrolling in this protocol will experience. As a result, the protocol will also assess sensitivity to this unique form of stress and will obtain additional followup data from participants. This will provide data on brain function and clinical outcomes in children and adolescents as it relates to a wide range of stressful events, including those that are closely related to the pandemic. While the current study tests no hypotheses specifically related to the stress of the pandemic, the unique circumstances of the pandemic create opportunities for enhanced stress exposures that need to be quantified. This is necessary to fully capture relationships between stress exposure and both brain function as well as treatment response, the two main targets related to anxiety symptoms in the current protocol.

4.2.2. Memory: Considerable research implicates memory abnormalities in both mood and anxiety disorders. Both basic science and clinical studies elucidate factors contributing to these associations.

Mnemonic abnormalities are found in adults with major depression, panic disorder, and social phobia.^{13-16, 20, 23, 24, 30, 31, 33} Such patients tend to show both an absolute decrement in declarative memory³³ as well as a recall bias for emotionally-negative material, termed "emotional memory bias".^{14, 15, 31} While this bias has been demonstrated using both evocative words and pictures, evocative words pose problems for child-based studies, given developmental changes in abstract thought. As a result, the current study uses pictures to probe both general memory as well as emotional memory. Prior studies in adults have used both standard facial expressions of emotion²² as well as standard slides from the International Affective Picture Series (IAPS).²¹ Both sets of stimuli will be used in the current study. As in research on attention, research considers emotional memory to relate closely to stress hypersensitivity. As a result, data on emotional memory also quantifies brain function related to stress, including pandemic-related stress.

Considerable research delineates cortico-limbic circuits involved in emotional modulation of memory. Studies in rodents implicate the amygdala and prefrontal cortex,⁶¹⁻⁶³ while neuroimaging studies in adults implicate analogous structures in human emotional memory.⁶⁴ These imaging studies rely on face encoding or IAPS rating paradigms that will be employed in the current study.

Studies in both animals and adults suggest that effective treatment for mood and anxiety disorders alters functioning in brain circuits that regulate memory.^{20, 21, 23, 24, 26, 30, 61} Specifically, antidepressants reduce memory bias. These effects are thought to derive at least partially through moderation of activity in a circuit encompassing the basolateral amygdala, hippocampus, and prefrontal cortex.

4.3. Cognitive Processes and treatment in adolescents:

4.3.1. Cognition: While the evidence is less definitive, adolescents with mood and anxiety disorders, much like adults, also exhibit attention and memory bias. ^{35, 40-43, 45-47, 65-68} However, since most children with depression exhibit signs of anxiety, it is difficult to draw conclusions on the nature of specific association between attention bias and pediatric depression. Taken together, the available literature finds signs of developmental continuity in the cognitive correlates of mood and anxiety disorders. Moreover, recent brain imaging studies,⁶⁹ including preliminary studies emanating from the current protocol,^{65-68, 70} demonstrate perturbations in amygdala-prefrontal cortical circuitry in pediatric depressive and anxiety disorders.

4.3.2. Treatment: SSRIs are established treatments for adult depression and anxiety. Existing data suggest similar effects in youth.^{34, 36-39, 48} Two SSRIs possess FDA indications for pediatric obsessive-compulsive disorder (OCD).³⁸ Available data also document strong benefits in anxiety.^{36, 48} In other work, CBT shows promise in pediatric anxiety disorders and major depression. Nevertheless, due to the paucity of head-to-head trials, it remains unclear the degree to which specific treatments provide particular benefits for specific pediatric mental disorders. Recent work also suggests that the training of attention through cognitive remediation strategies may augment response of anxiety disorders to SSRIs or CBT. Thus, the current protocol also will implement attention retraining as part of treatment with SSRIs or CBT.

5. Study Objectives or Hypotheses:

The primary goal of the project is to document in pediatric mood and anxiety disorders perturbations in brain systems mediating attention, memory, and response to various motivational stimuli. As one secondary goal, the protocol also will examine the relationship between brain activation prior to treatment and response to treatment over eight weeks as well as changes in fMRI and M/EEG activation before and after treatment. This goal is considered secondary given the paucity of knowledge concerning both aspects of treatment as well as aspects of brain function in pediatric mood and anxiety disorders. In anxiety disorders, as an additional secondary goal, preliminary data will be gathered on the utility of computer-based training on cognitive tasks designed to increase response to CBT.

Finally, data also will be acquired in adults to test the hypothesis that pediatric mood and anxiety disorders exhibit similar perturbations as found in adult mood and anxiety disorders. This prediction is based on available data in separate studies of adolescents and adults that document parallels in the correlates of mood and anxiety disorders across development. These data also suggest that distinct cognitive factors distinguish anxious and depressed from healthy individuals. Namely, because attention bias more strongly relates to anxiety than depression, we hypothesize that brain circuits associated with enhanced attention bias can be differentially engaged among anxious and depressed youth and adults, with anxious groups appearing most different from healthy ones at both ages. Conversely, because memory bias more strongly relates to depression than anxiety, we hypothesize that brain circuits associated with memory bias can be differentially engaged among depressed and anxiety and depressed groups appearing most different from healthy groups. We hypothesize that brain circuits associated with abnormal neural responses on social interaction fMRI and M/EEG tasks.

5.1. Baseline Dysfunction in Disorders: Our primary goal is to compare functioning in the amygdala, ventral prefrontal cortex, and striatum in healthy and anxious or depressed youth. A secondary goal extends this work to adults. Prior studies suggest that mood and anxiety disorders are associated with deficits in attention, emotional memory, reward processing, and social interaction. Imaging studies in adults suggest that these deficits result from dysfunction in the amygdala and ventral prefrontal cortex. The current study will use fMRI and M/EEG to examine brain regions engaged by attention, emotional memory, reward-

processing, social interaction, and fear-conditioning paradigms in pediatric and adult depression and anxiety disorders. As noted above, these paradigms are designed to quantify aspects of brain function related to stress sensitivity and exposure. As a result, levels of stress sensitivity and exposure will also be quantified to explore the degree to which they mediator or moderate associations between brain function and pediatric anxiety or depression.

- We hypothesize that fMRI- and M/EEG-measured attention bias, emotional memory, social interaction, fear conditioning, and reward paradigms will engage cortico-limbic brain regions in both healthy and impaired subjects, both among youths and among adults. However, healthy and impaired groups will differ in the degree of amygdala, prefrontal, and striatal engagement.
- For attention bias and fear conditioning paradigms, this difference is expected to be most prominent in anxiety. Specifically, we hypothesize that adolescents and adults with anxiety disorders will exhibit enhanced amygdala and ventral prefrontal cortex activation when attending to threat cues. This enhanced activation will occur both relative to healthy individuals and relative to individuals with major depression.
- In adolescent and adult major depression, in contrast, we hypothesize that enhanced activation will occur during an emotional memory paradigm, manifest as greater amygdala and prefrontal cortex activation in successfully vs. unsuccessfully remembered emotional stimuli. This enhanced activation will occur both relative to healthy groups and relative to anxiety-disorder groups.
- For social interaction tasks, we expect to observe similar differences in anxiety and depression. Thus, both patient groups are hypothesized to differ from healthy subjects but not from each other.
- Finally, for reward tasks, we expect to observe reduced neural responses to reward stimuli and enhanced response to punishment stimuli in depression. Anxiety would be marked by enhanced response to both negative and positive incentives.

5.2. *Treatment:* Effective treatment ameliorates neuro-cognitive correlates of adult mood and anxiety disorders.^{21, 23-26} In children, studies document benefits of SSRIs and CBT but none examine the relationship between treatment and brain function, a secondary focus of the current study. These measures of brain function quantify aspects of stress sensitivity. As a result, levels of stress sensitivity also will be quantified to explore the degree to which they relate to anxiety treatment outcome and its relationship with brain function mediating the persistence and development of anxiety.

- We hypothesize that subjects who respond to treatment will differ from subjects who do not, based on their pattern of behavior and fMRI and M/EEG activation pre-treatment. Specifically, we predict that responders and non-responders will differ in their pattern of attention bias, memory performance, and amygdala/prefrontal cortical activation.
- We also hypothesize that effective treatment will reduce attention-related amygdala and prefrontal cortex dysfunction in adolescents with anxiety disorders. Of note, this hypothesis will be tested only in youth; adults will not be re-tested after treatment, nor will analyses compare adults and adolescents after treatment. Specifically, we hypothesize that anxiety-disorder subjects who respond to treatment, relative to those who do not respond, will differ in fMRI and M/EEG amygdala and ventral prefrontal activations when attending to threat, such that only non-responders will continue to differ from healthy adolescents. In depression, we expect successful treatment to normalize abnormalities in amygdala and prefrontal activation in an emotional memory paradigm.

The project will test these hypotheses by studying three groups of youths: i) psychiatrically healthy youth ["healthy"]; ii) youth without major depression but with social phobia, separation anxiety, or generalized anxiety disorders ["anxious"]; iii) youth with major depression, with or without social phobia, separation

anxiety, generalized anxiety disorders ["depressed"]. In addition, to document commonalities and differences with adults, we will study an additional three groups: iv) adults with an anxiety disorder ["anxious"]; v) psychiatrically healthy adults ["healthy"]; vi) adults with major depression.

Prior to treatment, subjects will undergo fMRI and M/EEG scanning while performing paradigms hypothesized to differentiate relevant groups. Subjects with mood and anxiety disorders will then be treated for eight weeks. Adolescent patients will be re-studied using the fMRI and M/EEG attention and emotional memory paradigms. In all subjects, data for social interaction and reward tasks only will be acquired once, prior to treatment.

6. Subjects

6.1. Description of Study Populations:

A total of 360 juvenile subjects will be studied comprehensively, comprising groups of "healthy," "anxious," and "depressed" youth. Of note, we anticipate enrolling far more than 360 subjects (see accrual numbers; total accrual ceiling is set to be n=2530), as not all subjects enter all phases of the study. For example, some subjects may remit during the initial pre-treatment phases of the study. Such subjects will, of course, not receive treatment. Other subjects may only tolerate a portion of the procedures proposed here. By "studied comprehensively", we mean that we plan to obtain data for *each* key assessment measure in a total of 360 juveniles, as stratified below.

Based on prior studies, 80% of the depressed subjects are expected to meet criteria for a current anxiety disorder. Thus, our goal is to collect data for each measure among 20 depressed adolescents without an anxiety disorder as well as 40 depressed adolescents with a comorbid anxiety disorder. In terms of anxiety disorders, we expect to study on each of our tasks approximately 80 subjects with social phobia, 40 subjects with separation anxiety disorder, and 80 subjects with generalized anxiety disorder. These numbers exceed n=150 due to comorbidities. Of note, we plan to directly contrast specific anxiety disorders, particularly generalized and social anxiety disorders. Thus, a relatively large sample size is needed.

Hypotheses for studies in adult mood and anxiety disorders are identical to those in youth. Moreover, we expect comparable effect sizes for between-group comparisons of healthy and impaired adults as found in healthy and impaired adolescents. As a result, we will study 60 adults with anxiety disorders, of whom approximately 30 will have social phobia; 30 will have generalized anxiety disorder; and 20 will have panic disorder. This will provide sufficient data for power analyses in specific anxiety disorders.

The rationale for sample sizes follow from prior treatment and neuropsychological studies (see power analysis section). The current project is powered to examine the neurobiology of each task in both pediatric mood and anxiety disorders, considered individually. This represents the main goal of the study. Given heterogeneity in treatment outcome, it is not feasible to study sufficient numbers of subjects to provide definitive insights on prediction of treatment outcome. Thus, the study is not designed, as a primary goal, to examine prediction of response to one or another treatment.

In addition to these 650 juveniles, 650 psychiatrically healthy adult volunteers will be studied using similar procedures to those used among the psychiatrically healthy juveniles. Finally, 100 adults with major depression and 60 adults with an ongoing anxiety disorder (panic disorder, social phobia, or generalized anxiety disorder) will be studied using these methods. These 120 adults will undergo the procedures described in this study. Adults with major depression or anxiety will be treated with fluoxetine by a member

of [name] staff. Studies in adults will not acquire data after treatment. Hypotheses and statistical power considerations are identical in studies of adults and youths.

As of June 3, 2011, 1196 subjects have been accrued into the protocol with a ceiling of 2530 subjects. This includes 1141 subjects who are study completers.

6.2. Inclusion Criteria:			
INCLUSION CRITERION	COMMENTS		
ALL JUVENILE SUBJECTS			
Age: 8-17 (subjects who consent as 17-year-olds but turn			
18 during the course of the study will be eligible to			
complete all procedures completed by other subjects who			
consent as 17-year-olds but do not turn 18).			
	Parents will provide consent; minors will provide assent		
	Assessment relies on either a WASI or assessment by		
	trained clinical staff during the subject's screening visit.		
	Completion of required activities during the screening		
	visit requires an IQ above 70.		
	Tasks in this protocol have not been validated in		
	anguages other than English		
ALL ADULT SUBJECTS			
Age: 18-65			
Consent: can give consent			
- •	Assessment relies on either a WASI or assessment by		
	trained clinical staff during the subject's screening visit.		
	Completion of required activities during the screening		
	visit requires an IQ above 70.		
	Tasks in this protocol have not been validated in		
ALL SUBJECTS WITH AN ANXIETY DISORDER	anguages other than English		
	Based on K-SADS (juveniles) or SCID (adults)		
Anxiety, Generalized Anxiety Disorder, or Panic Disorder	based on R-SADS (Juvennes) of SCID (adults)		
	This will be documented by clinician review with patients and		
	their families during at least two visits with families.		
	This will be documented by clinician review with patients and		
distress or impairment from anxiety t	their families during at least two visits with families.		
ALL SUBJECTS WITH A MOOD DISORDER			
	Based on K-SADS (juveniles) or SCID (adults)		
	This will be documented by clinician review with patients and		
	their families during at least two visits with families.		
	This will be documented by clinician review with patients and		
	their families during at least two visits with families.		
ALL PREVIOUSLY ENROLLED ADOLESCENT			
PATIENTS, CHILD AND ADULT HEALTHY			
VOLUNTEERS, AND ALL HEALTHY			
VOLUNTEERS TURNED PATIENTS			
Diagnosis: Current Diagnosis of Social Phobia, Separation	Based on K-SADS (juveniles) or SCID (adults)		
Anxiety, Generalized Anxiety Disorder, or Panic Disorder;			
No current diagnosis			

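### Section 6.1 states sample sizes (650 juveniles, 650 healthy adults, 120 adult patients) that contradict the plan's other counts (360, 150, 160), and section 11.5 adds two conflicts in the depression groups

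*Combined protocol and SAP*

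**What the plan says.** **Title page and Precis.** The accrual table lists six groups with numbers to be recruited and to be studied, totalling 2,530 and 670. The Precis repeats the second column: "We seek to comprehensively study 150 juveniles with only a current anxiety disorder, 60 juveniles with current major depression", 150 healthy juveniles, and "100 adults with major depression, 60 adults with an anxiety disorder, and 150 adults with no psychiatric disorder".

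**Section 6.1, opening.** "A total of 360 juvenile subjects will be studied comprehensively". This is explained as having data on every key assessment measure. The next paragraph divides the depressed youth into 20 without and 40 with an anxiety disorder.

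**Section 6.1, fifth paragraph.** "In addition to these 650 juveniles, 650 psychiatrically healthy adult volunteers will be studied using similar procedures". The paragraph continues "Finally, 100 adults with major depression and 60 adults with an ongoing anxiety disorder", and the next sentence reads "These 120 adults will undergo the procedures described in this study".

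**Section 6.1, last paragraph.** At 3 June 2011, 1,196 subjects had been accrued. "This includes 1141 subjects who are study completers". The term is not defined.

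**Section 11.5.** Power is based on n=45 per contrast. For depression as a whole, n is given as 60 in youths and in adults. When depressed subjects are divided by anxiety status, n is 30 in each part, for both age groups.

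**The concern.** Section 6.1 is the operative description of who will be studied, so its numbers should agree with the accrual table, the Precis and the sample size section. Three of them do not. Two of those three conflicts arise inside section 6.1 itself: 360 juveniles become 650, and 100 plus 60 adult patients become 120.

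Section 11.5 carries further sizes for the depression groups that agree with neither the table nor section 6.1. Correcting section 6.1 alone would therefore leave the plan inconsistent.

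What is at stake is the planned size of the adult comparison and patient groups, the juvenile total, and the split of depressed youth used for the sub-analysis by anxiety status. A reader of section 6.1 alone would take away the wrong figures.

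**Working it through.** **1. Reproduce the plan's totals.** Rows are in table order: juvenile anxiety, depression, healthy; adult depression, anxiety, healthy.

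- Recruited: 600 + 80 + 750 + 150 + 200 + 750 = 2,530, as printed.
- Studied: 150 + 60 + 150 + 100 + 60 + 150 = 670, as printed.

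The table is sound, and the Precis gives the same six studied figures. The sums 360 and 160 used below are not printed in the table or Precis; 360 is printed in section 6.1.

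**2. Set section 6.1 against both columns.**

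| Group | Section 6.1, fifth paragraph | Studied | Recruited |
|---|---|---|---|
| Juveniles | 650 | 150 + 60 + 150 = 360 | 600 + 80 + 750 = 1,430 |
| Healthy adults | 650 | 150 | 750 |
| Adult patients | 120 | 100 + 60 = 160 | 150 + 200 = 350 |

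Differences from the studied column: 650 − 360 = 290; 650 − 150 = 500; 160 − 120 = 40. The section 6.1 figures total 650 + 650 + 120 = 1,420 (1,460 with 160), which is neither 670 nor 2,530.

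**3. Could another grouping explain them?**

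- 650 from the studied column would mean leaving out rows worth 670 − 650 = 20, but the smallest row is 60.
- 650 from the recruited column cannot include a 750. Of the rest, 600 alone is too small, 600 + 80 = 680 is too large, and without the 600 the most is 80 + 150 + 200 = 430.
- 120 arises only as 60 + 60, juvenile depression plus adult anxiety, which is not the group named.

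**4. Section 11.5 against the rest.**

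- Depressed adults: 60 in section 11.5; 100 in the table, the Precis and section 6.1.
- Depressed youth: 30 + 30 = 60 in section 11.5; 40 + 20 = 60 in section 6.1. The total agrees and the split does not.

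Sixty depressed plus 60 anxious adults would give 120, so the stray 120 may be left over from a smaller adult depression target. That is an inference; the documents do not say so.

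**5. Effect on the power statement.** Section 11.5 uses n=45 per group and d = 0.8 to 1.2. With two-sided alpha 0.05 (assumed; section 11.5 gives none), the noncentrality at d = 0.8 is 0.8 × √(45/2) = 3.79 and power is 0.967. At d = 1.2 power is about 1.0. The claim of more than 0.80 is reproduced, and none of the disputed totals enters it.

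**6. Effect on the detectable difference in adults.** For 80% power, d ≈ (1.960 + 0.842) × √(1/n₁ + 1/n₂):

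- 60 anxious against 150 healthy: 0.43; against 650: 0.38.
- 100 depressed against 150 healthy: 0.36; against 650: 0.30.
- 60 depressed (section 11.5) against 150 healthy: 0.43.

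All lie well below the 0.8 to 1.2 that the plan aims to detect.

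**7. The completer count.** 1,141/1,196 = 95.4%; 1,141 − 670 = 471; 1,141/670 = 1.70. The table's own ratio of studied to recruited is 670/2,530 = 26.5%.

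**The case against.** The strongest reply is that the targets are fixed and legible. The six group sizes are identical in the accrual table and the Precis, and section 6.1 repeats and defines the juvenile 360. The primary juvenile groups (150, 60, 150) are not contradicted at group level; one sentence carries a different aggregate with no breakdown. The adult figures serve a secondary goal. Power is set per contrast at n=45, below every group in the table, and section 11.5 concedes that smaller cells are underpowered. All of this stands. It limits the consequences but does not make the figures in section 6.1 right.

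A second reply is that the 650s might be recruitment numbers. This fails, because recruitment is 1,430 juveniles and 750 healthy adults.

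A reader might go further and infer that the study passed its target in 2011, since 1,141 exceeds 670. The documents do not support this. The 670 are people to be studied comprehensively, which for juveniles means data on each key measure. Study completers is undefined and may be looser. A 95.4% rate sits badly with the Precis, which expects most subjects not to finish every procedure, so the two terms probably differ. The count is also explicitly dated, so it is old rather than false.

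**Conclusion.** The point holds as a set of wrong stated sample sizes. In section 6.1, the juvenile total is off by 290, healthy adults by 500 and adult patients by 40. In section 11.5, depressed adults are 60 against 100 elsewhere, and each part of the depressed-youth split is off by 10. This takes the table and Precis as the reference, because they agree with each other and with the opening of section 6.1. If 650 was intended, the error lies in them instead.

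Three stronger inferences are not supported. The plan does not lack a target, since the table and Precis give one. The stated power is not undermined: it rests on n=45 and d = 0.8 to 1.2, and moving healthy adults from 150 to 650 changes the detectable d only from 0.43 to 0.38 (anxious) or from 0.36 to 0.30 (depressed). Nor do the mismatches show that contrasts can be re-run at will as accrual proceeds; whether the plan sets an analysis cut-off is a separate question that matching numbers would not settle.

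**What to change.** 1. In the fifth paragraph of section 6.1, change the counts to 360 juveniles, 150 healthy adults and 160 adult patients. If 650 is intended for either group, correct the accrual table, the Precis and the opening of section 6.1 instead.
2. In section 11.5, align the depression sizes with the same counts: 100 depressed adults (or change the 100 elsewhere), one agreed split of the 60 depressed youth by anxiety status, and an adult split that adds up to the adult total. The n=45 statement can stay.
3. As a secondary tidy-up, define study completers relative to studied comprehensively, and replace the June 2011 sentence with a current count on that definition, preferably by group.

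The cost is protocol wording plus one count from the existing database. No procedure or analysis changes.
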